2.6. Analysis Sets

2.6.1. Intent-to-Treat Analysis Set

The intent-to-treat (ITT) analysis set includes all the subjects who were randomized and received at least 1 dose of treatment subsequent to randomization in the study. Efficacy data up to the last dose date of the treatment are included. The safety analysis (including all data collected at the 30-day FU visit) is also performed on this analysis set.

2.6.2. Per Protocol Analysis Set

An analysis based on the per protocol (PP) population will also be performed to investigate the impact of excluding subjects with major protocol violations and to evaluate the robustness of the analysis results. The PP population will include all subjects who:

- (1) are randomized into the study,
- (2) have received ≥ 1 dose of treatment in the study, and
- (3) without any major protocol deviation that is considered to potentially affect efficacy outcomes. Specific details are provided in Attachment 1.

The PP analysis set is the secondary analysis set for efficacy analysis. The per protocol (PP) set is defined as the ITT analysis set minus subjects with major protocol violations as listed in Attachment 1.

2.6.3. Bone Investigation Substudy Analysis Set

The bone investigation substudy (BIS) analysis set includes all subjects in the ITT set and having at least one post-baseline value either in biomarker or in BMD data. The bone investigation analysis will be performed on this analysis set.

2.7. Definition of Subgroups

2.7.1. Subgroups for Efficacy Analyses

- Adherence based on D/C/F/TAF (i.e., from reference) drug accountability (>95%: adherent, $\leq 95\%$: non-adherent, missing/unknown)
- Reference viral load
 - For Initial D/C/F/TAF group the screening and baseline viral load
 - <50; if all screening and baseline viral load values are below 50 copies/mL
 - ≥ 50 ; if at least one viral load value during screening or baseline ≥ 50 copies/mL)
 - For Late Switch group, the reference viral load
 - <50 copies/mL
 - ≥ 50 copies/mL
- CD4+ count at reference (<200, ≥ 200 [200 $\leq x < 350$, 350 $\leq x \leq 500$, >500] cells/mm³)
- Race (American Indian or Alaska Native, Asian, Black or African American, White, Native Hawaiian or other Pacific Islander, Other, non-Black or African American)
- Ethnicity (Hispanic or Latino, non-Hispanic or Latino)
- Gender (Female, Male)
- Age group (≤ 50 , >50 years)
- Region (Europe, North America)
- Re-classified bPI at screening (see section 2.5):
 - DRV once daily with rtv or COBI; ATV with rtv or COBI; LPV with rtv
 - ATV with rtv or COBI, or LPV with rtv
 - DRV with rtv; DRV with COBI
- Booster at screening (ritonavir or cobicistat)
- Number of previous ARVs used (3, 4, 5, 6, 7, >7) and previous PI, N(t)RTI or NNRTI used (0, 1, 2, 3, 4, >4)

- Previous ARV failure and previous PI, N(t)RTI or NNRTI failure (0, ≥ 1)
- WHO Clinical Staging of HIV/AIDS
- Viral blip (see section 4.6.1) during first 48 weeks:
 - Yes, if subject experience at least 1 viral blip during the first 48 weeks of the study
 - No, otherwise
- For the Late Switch group only:
 - Protocol-defined virologic rebound during first 48 weeks
 - Yes, if subject experience a protocol-defined virologic rebound during the first 48 weeks of the study
 - No, otherwise

2.7.2. Subgroups for Safety Analyses

- Race (American Indian or Alaska Native, Asian, Black or African American, White, Native Hawaiian or other Pacific Islander, Other, non-Black or African American)
- Ethnicity (Hispanic or Latino, non-Hispanic or Latino)
- Gender (Female, Male)
- Age group (≤ 50 , > 50 years)
- Region (Europe, North America)
- Re-classified bPI at screening:
 - DRV once daily with rtv or COBI; ATV with rtv or COBI; LPV with rtv
 - ATV with rtv or COBI, or LPV with rtv
 - DRV with rtv; DRV with COBI
- Booster at screening (ritonavir or cobicistat)
- Reference eGFR_{CG} (< 70 , ≥ 70 mL/min)
- WHO Clinical Staging of HIV/AIDS

Subgroups for Bone Investigation Analyses:

- bPI at screening
- Race (American Indian or Alaska Native, Asian, Black or African American, White, Native Hawaiian or other Pacific Islander, Other, Non Black)
- Gender
- Reference BMI ((underweight (< 18.5 kg/m²), normal range (18.5 to < 25.0 kg/m²), overweight (≥ 25.0 kg/m²) and obese (≥ 30.0 kg/m²))

- Age group (≤ 50 , > 50 years)
- Current smoking status (yes/no)

2.8. Re-classification of Stratification Factor for Purpose of Analysis

For the purpose of analysis the stratification factor (bPI) was re-classified based on the value from the history of ARV therapy data at screening.

The re-classified stratification factor is used for analysis..

2.9. Reference

For Initial D/C/F/TAF group, reference is the comparative treatment phase baseline as in Week 48 analysis. For the late switch group two references will be used: (1) comparative treatment baseline will be used as reference for the period up to the switch; (2) the last value prior to the switch will be used as reference for the extended treatment phase.

3. SUBJECT INFORMATION

3.4. Demographics and Baseline Characteristics

These parameters will not be included in this analysis, because no new subjects were recruited since the Week 48 analysis.

3.5. Disposition Information

A tabulation of the total number (with percentages) of subjects screened, randomized and not treated, randomized and treated and treated in extended treatment phase will be provided.

Tabulation per treatment arm and overall of the number of subjects who have completed the treatment/ extended treatment phase, who are ongoing, and who have discontinued the trial before Week 96 visit, with the reason for discontinuation will be provided.

A Kaplan-Meier graph for the time to Discontinuation (any reason) will be included.

3.6. Treatment Adherence

Treatment adherence based on drug accountability will be summarized by means of descriptive statistics and frequency tabulations. Cumulative treatment adherence will be calculated from baseline through Week 96 for the Initial Switch to D/C/F/TAF arm; from baseline to the switch, and again from the switch to Week 96 for the Late Switch to D/C/F/TAF arm. Cumulative treatment adherence will be determined (derivation i).

The following parameters are derived:

Amount to be taken through switch/Week 96 = (number of days since start of treatment/switch \times number of tablets to be taken per day).

Number of days since start of treatmentswitch is based on (whichever comes sooner):

- last study medication intake (if available) or, in case subject discontinued and last study medication intake is missing, the last visit date prior to withdrawal will be used.
- Switch/Week 96 visit date

In addition (derivation ii), the cumulative treatment adherence up to time point where not more than one bottle is missing, or if available, up to switch/Week 96, whichever comes sooner, will be calculated.

Actual amount taken = (number of tablets dispensed – number of tablets returned), summed over time points up to the time point of interest.

Level of adherence = (actual amount taken / amount to be taken) × 100%

Treatment adherence is defined as:

- adherent: the level of adherence is >95%,
- non-adherent: the level of adherence is ≤95%.

Additionally, following categories of level of adherence will be defined:

- >95%
-]80%; 95%]
-]65%; 80%]
-]50%; 65%]
- ≤ 50%

Interruptions (for AEs) are not to be taken into account for the calculation of adherence, i.e. they will not be subtracted from the amount to be taken.

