### 9.3. Management of Virologic Rebound

Subjects will be considered to have virologic rebound if they have a confirmed (2 consecutive tests) HIV-1 RNA  $\geq$ 50 copies/mL at a scheduled or unscheduled visit after maintaining HIV-1 RNA <50 copies/mL.

Subjects with HIV-1 RNA  $\geq$ 50 copies/mL will be managed as follows:

- If a single viral load measurement is ≥50 copies/mL after having previously been <50 copies/mL, subjects should be contacted preferably within 48 hours to assess potential causes (eg, active substance abuse, depression, other intercurrent illnesses, lack of adherence) and adequate intervention should be provided (eg. additional adherence counsellation). HIV-1 RNA testing should be repeated at a scheduled or unscheduled visit 2 to 4 weeks after the date of the initial viral load result of HIV-1 RNA ≥50 copies/mL.
- Upon confirmation of HIV-1 RNA ≥50 copies/mL, potential causes of virologic rebound should be documented. Assessment should include adherence, concomitant medication, and comorbidities (eg, active substance abuse, depression, other intercurrent illnesses, lack of adherence).
- If virologic rebound is confirmed at the scheduled or unscheduled visit and the HIV-1 RNA value is ≥400 copies/mL, the blood sample from that visit or a following visit with HIV-1 RNA ≥400 copies/mL will be used for HIV-1 genotypic testing. Phenotypic resistance testing may be done upon request of the study virologist (see also Section 9.2.2).
- If genotypic/phenotypic resistance to study drugs is determined, study drugs may be discontinued at the discretion of the investigator. In case of early discontinuation, and HIV-1 RNA ≥400 copies/mL, an HIV-1 genotypic resistance report, if available, will be forwarded to the investigator in order to assist in the selection of a new ARV regimen.
- If no resistance is detected from genotypic/phenotypic testing, the subject may remain on study drug and the viral load will be further monitored. Genotype/phenotype testing at other time points may be requested if deemed necessary by the protocol virologist. Investigators should carefully evaluate the benefits and risks of remaining on study drug for each individual subject and document this assessment in the on-site medical record. Investigators who opt to discontinue study drugs for an individual subject must discuss this with the sponsor's medical monitor prior to study drug discontinuation.

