1.1. Trial Objectives

The primary objective of this study was to demonstrate noninferiority in efficacy of a D/C/F/TAF once-daily single-tablet regimen relative to continuing the current bPI combined with FTC/TDF in virologically-suppressed (HIV-1 RNA <50 copies/mL) HIV-1 infected subjects, in regard to the proportion of virologic rebounders (defined as having confirmed HIV-1 RNA \geq 50 copies/mL through Week 48, or in case of early discontinuation a last single viral load of HIV-1 RNA \geq 50 copies/mL) with a maximum allowable difference of 4%.

The secondary objectives of this study were:

- To evaluate superiority of switching to a D/C/F/TAF once-daily single-tablet regimen versus continuing the current bPI combined with FTC/TDF in regard to the proportion of virologic rebounders through Week 48, in case noninferiority is established;
- To evaluate the proportion of rebounders through Week 48 in the 2 treatment arms;
- To evaluate efficacy as determined by continued suppression of HIV-1 RNA (<20, <50, and <200 HIV-1 RNA copies/mL as defined by the FDA Snapshot analysis and time to loss of virologic response [TLOVR] algorithm) at Weeks 24 and 48 in the 2 treatment arms;
- To evaluate the safety and tolerability of the D/C/F/TAF regimen through 24 and 48 weeks of treatment;
- To evaluate the change from baseline in serum creatinine, eGFR for creatinine clearance (eGFR_{cr}, by Cockcroft-Gault and by Chronic Kidney Disease Epidemiology Collaboration [CKD-EPI]) and eGFR for cystatin C clearance (eGFR_{cyst}, by CKD-EPI) in the 2 treatment arms at Weeks 24 and 48;
- To evaluate the change from baseline in renal biomarkers at Weeks 24 and 48;
- To evaluate immunologic changes (CD4+ cell count) through 24 and 48 weeks of treatment in the 2 treatment arms;
- To evaluate adherence through drug intake (as derived by drug accountability data), and explore correlation with primary efficacy outcome;
- To evaluate resistance in subjects who show virologic rebound through Weeks 24 and 48 in the 2 treatment arms;
- To evaluate the steady-state pharmacokinetics of DRV in the D/C/F/TAF arm.

Secondary objectives in a bone investigation substudy performed at selected study sites:

- To evaluate the changes from baseline in bone biomarker levels at Weeks 24 and 48;

- To evaluate the safety of the 2 treatment arms as determined by the percent change from baseline in spine and hip bone mineral density (BMD) and changes in associated T-score at Weeks 24 and 48.

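### Adherence is cumulated without stopping at rebound or blip, so a subject with an early event who stays on drug and then takes it better can be classed as adherent

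*SAP*

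**What the plan says.** SAP 3.6 derives pill-count adherence as tablets taken divided by tablets due. For initial switchers, "Cumulative treatment adherence will be calculated from baseline through Week 96 for the Initial Switch to D/C/F/TAF arm". For late switchers it is calculated "from baseline to the switch, and again from the switch to Week 96 for the Late Switch to D/C/F/TAF arm". The window closes before the switch or Week 96 visit only at the "last study medication intake (if available) or, in case subject discontinued and last study medication intake is missing, the last visit date prior to withdrawal". A second derivation gives "the cumulative treatment adherence up to time point where not more than one bottle is missing". The cut is set as "adherent: the level of adherence is >95" per cent, and anything at or below 95% is non-adherent. No rule closes the window at a virologic event.

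The measure is then related to virologic outcome in two places:

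- SAP 2.7.1 lists, as an efficacy subgroup, "Adherence based on D/C/F/TAF (i.e., from reference) drug accountability", split at 95%.
- SAP 4.6.2 (Viral Blip) presents adherence by rebound, blip or no blip, and applies a within-group CMH test to compliance above 95%.

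Under SAP 4.6.1 a confirmed rebound at any time from reference counts as a rebound through Week 96. Protocol 9.3 says that after a first value of 50 copies/mL or more "adequate intervention should be provided (eg. additional adherence counsellation". It also allows a subject with confirmed rebound and no detected resistance to stay on study drug.

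**The concern.** To describe whether poor adherence goes with rebound, the adherence figure should describe the time before the rebound. For a subject who rebounds early and continues, much of the figure in SAP 3.6 describes the time afterwards, possibly after a step meant to improve adherence. The grouping variable is then partly a consequence of the outcome.

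Blips have the same problem. By definition a blip is followed by a value below threshold, so these subjects generally have follow-up after the event, and the same contact and intervention guidance applies after the first raised value.

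Rebounders are also scored on different footings. Those who stop drug are scored to last intake, which is essentially their pre-event adherence. Those who continue are scored on a mixture of before and after. One table row then holds two different quantities, and some events preceded by poor adherence can be counted in the adherent group.

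**Working it through.** The plan states no figure for this point, so there is none to reproduce. The check uses the SAP 3.6 formula in time-weighted form.

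**Inputs from the documents**
- Window T: 96 weeks for Initial Switch; 96 − 52 = 44 weeks for Late Switch on D/C/F/TAF (switch visit at Week 52).
- Cut-off: above 95%.

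**Assumed inputs (not in the documents)**
- a = adherence before the event.
- b = adherence after the event, shown at 100%, 98% and 95%.
- t = weeks from reference to the event, with the subject staying on drug to Week 96.

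**Formula.** Cumulative adherence = [a·t + b·(T − t)] / T. The subject is classed as adherent when this exceeds 0.95:
- b = 100%: a > 1 − 0.05·T/t
- b = 98%: a > 0.98 − 0.03·T/t
- b = 95% or less: a weighted average of two values at or below 95% cannot exceed 95%, so nobody with a at or below 95% is reclassified.

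**Pre-event adherence above which the subject is classed as adherent**

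| Arm and event time | b = 100% | b = 98% |
|---|---|---|
| Initial Switch, Week 8 | 40% | 62% |
| Initial Switch, Week 12 | 60% | 74% |
| Initial Switch, Week 24 | 80% | 86% |
| Initial Switch, Week 36 | 86.7% | 90% |
| Initial Switch, Week 48 | 90% | 92% |
| Initial Switch, Week 72 | 93.3% | 94% |
| Late Switch, 8 weeks after switch | 72.5% | 81.5% |
| Late Switch, 20 weeks after switch | 89% | 91.4% |
| Late Switch, 32 weeks after switch | 93.1% | 93.9% |

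For example, at Week 12 with b = 100%: 1 − 0.05 × 96/12 = 0.60. In the Late Switch arm at 8 weeks: 1 − 0.05 × 44/8 = 0.725.

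**Individual cases, Initial Switch, b = 100%**
- a = 70%, Week 12 event: (0.70 × 12 + 84)/96 = 96.25%, adherent. Cut at the event: 70%, non-adherent.
- a = 90%, Week 24 event: (0.90 × 24 + 72)/96 = 97.5%, adherent. Cut at the event: 90%, non-adherent.
- a = 80%, Week 24 event: (0.80 × 24 + 72)/96 = 95.0%, non-adherent either way, because the cut is strictly above 95%.
- a = 80%, Week 48 event: (0.80 × 48 + 48)/96 = 90.0%, non-adherent either way.
- a = 80%, drug stopped at the event: the score stays 80%.

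**The case against.** The strongest reply is that reclassification needs three things together: a fairly early event, continued treatment and better intake afterwards. That is correct. Two of the three rebound routes in SAP 4.6.1 (discontinuation with a raised last value, and a raised last value at the Week 96 cut-off) leave essentially no post-event adherence time. The documents give neither adherence levels nor event timing, so the number of subjects affected is unknown.

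A second reply is that little depends on the result. SAP 1.3 has no formal hypothesis at Week 96 and SAP 4.4.1 calls all efficacy results descriptive. This limits the importance of the point. It does not remove it, because SAP 4.6.2 still attaches a CMH test to compliance above 95%.

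A reader might also infer more than the documents support:
- **That the trial objective on adherence is compromised.** The objective is to "explore correlation with primary efficacy outcome". That outcome is rebound through Week 48, and SAP 4.5.1 leaves its analysis outside this SAP. How adherence was measured for it cannot be judged from these documents.
- **That every efficacy subgroup result is affected.** Snapshot at Week 96 uses the last value in Weeks 90–102, or the discontinuation status. Cumulative adherence to Week 96 or last intake covers the time leading up to that outcome and suits it.
- **That the association would be reversed.** The arithmetic moves individual subjects between groups. It shows possible dilution, not a change of sign.
- **That counselling is compulsory.** Protocol 9.3 says an intervention should be given and names counselling as an example.

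**Conclusion.** The point holds as a minor one. Under the plan as written, a subject with an early confirmed rebound or blip who stays on drug can be classed as adherent despite adherence at or below 95% before the event. The effect is largest for early events and shrinks as the event moves later: with perfect intake afterwards in the Initial Switch arm, the required pre-event level rises from above 60% at Week 12 to above 90% at Week 48. In the Late Switch arm the shorter window, about 44 weeks, limits it further.

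The finding rests on assumed adherence before and after the event, and it disappears if later adherence is 95% or less. It can dilute the adherence comparison in the rebound subgroup analysis (SAP 2.7.1) and in the rebound, blip or no-blip table with its CMH test (SAP 4.6.2). The documents do not support saying that poorly adherent rebounders are classed as adherent in general.

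**What to change.** For the rebound and blip analyses only, add a second adherence figure: cumulative adherence from reference to the first rebound or blip time point, or to last intake if the subject stopped. Compare it with subjects still event-free, cumulated over the same visits. The matching matters, because cutting only the subjects with events would leave unequal windows. A single landmark, such as adherence to Week 24 against rebound after Week 24, is a poor substitute: it drops the early events where the problem is largest.

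Keep the Week 96 cumulative figure for the compliance summary and for Snapshot at Week 96.

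No new data are needed. SAP 4.6.1 already derives the first rebound time point, and the protocol's Time and Events Schedule has drug accountability at the treatment and extension visits through Week 96. The cost is one extra derivation, some SAP wording, and shorter, noisier pill-count windows for early events.

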ATTACHMENT 1: PREDEFINED MAJOR PROTOCOL DEVIATIONS-BASED ON THE CURRENT LIST

The predefined major protocol deviations of this study are described in the Protocol Deviation Criteria document. The deviations that are considered to have an (possible) impact on efficacy are a subset of the predefined major protocol deviations and are indicated with 'Yes' below (column 'Exclude from Per Protocol Analysis') and if such deviations are reported for a subject, the subject will be excluded from the PP analysis.

In addition to the table below, subjects with a baseline HIV-1 RNA value ≥ 50 copies/mL and subjects with treatment adherence $< 65\%$ (Late Switch group will use worst adherence from baseline to switch and from switch to week 96) per derivation ii will also be excluded from the per-protocol analysis set.

Sequence No.	Description	Protocol Deviation coded term (DVDECOD)	Exclude from PP
1	The subject has not been treated with a stable ARV regimen consisting of a bPI (limited to DRV or ATV with rtv or COBI, or LPV with rtv) combined with FTC/TDF only for at least 6 consecutive months preceding the screening visit.	Entered but did not satisfy criteria	Yes
2	
 • During the 12 months preceding screening while on stable ART: 
 - The subject did not have at least 1 plasma HIV-1 RNA measurement < 50 copies/mL (or HIV-1 RNA undetectable by a local HIV-1 RNA test) occurring between 12 and 2 months prior to the screening visit while on the stable ARV regimen or - The subject has a documented plasma HIV-1 RNA concentrations ≥ 200 copies/mL. or - The subject has documented more than 1 plasma HIV-1 RNA concentrations ≥ 50 copies/mL (or HIV-1 RNA detectable by a local 	Entered but did not satisfy criteria	Yes

	
HIV-1 RNA test)
 
or
 
 - The subject has at least 1 single documented plasma HIV-1 RNA concentrations ≥ 50 copies/mL and < 200 copies/mL but had no subsequent VL measurement < 50 HIV-1 RNA copies/mL at the latest 2 months prior to screening 
or
 
 • At the screening visit has HIV-1 RNA ≥ 50 copies/mL. 		
3	The subject has a history of failure on DRV treatment or any of DRV RAMs (V11I, V32I, L33F, I47V, I50V, I54M, I54L, T74P, L76V, I84V, L89V) (if historical genotypes are available)	Entered but did not satisfy criteria	Yes

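### Derivation (i) of adherence in SAP 3.6 counts unreturned tablets as taken over a denominator that stops early, so a subject who leaves without returning drug can be classed above 95% adherent

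*SAP*

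**What the plan says.** SAP 3.6 defines the score as "Level of adherence = (actual amount taken / amount to be taken"), times 100%. The numerator is tablets dispensed less the "number of tablets returned), summed over time points up to the time point of interest". The denominator is days since the start of treatment (or since the switch) times tablets per day. Those days run to the last study medication intake; "in case subject discontinued and last study medication intake is missing, the last visit date prior to withdrawal will be used". They never run past the switch or Week 96 visit. A subject is "adherent: the level of adherence is >95" percent, with no upper limit.

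The section then adds a second measure: "In addition (derivation ii), the cumulative treatment adherence up to time point where not more than one bottle is missing". Attachment 1 uses this one for a per-protocol exclusion: subjects below 65% "per derivation ii will also be excluded from the per-protocol analysis set".

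The >95% cut is used in two other places. SAP 2.7.1 defines an efficacy subgroup, "Adherence based on D/C/F/TAF (i.e., from reference) drug accountability", with the classes >95%, ≤95% and missing/unknown. SAP 4.6.2 describes adherence by rebound, blip or no blip and applies a within-group CMH test to the >95% class. Neither names derivation (i) or (ii).

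**The concern.** Numerator and denominator need not cover the same period. When a subject attends a visit, is given drug and is not seen again, the tablets dispensed may enter the numerator while no later day enters the denominator. More generally, any bottle that does not come back is credited as swallowed.

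A stated secondary objective (Protocol 2.1, SAP 1.1) is to explore how adherence relates to the efficacy outcome. SAP 4.6.1 counts a subject who discontinues with a last on-treatment HIV-1 RNA at or above the threshold as a rebounder. Some rebounders may therefore be the same early leavers whose adherence is inflated. Moving them into the adherent class would weaken any adherence–rebound association and flatter the adherence summary. That direction is plausible; the documents do not establish it.

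**Working it through.** The documents state no adherence figure to reproduce, so the check works the SAP 3.6 ratio directly.

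**Inputs from the documents.** One D/C/F/TAF tablet daily (Protocol 3.2.1). Dispensing at each visit except Week 2 (Protocol 5). Visits at Weeks 2, 4, 8, 12, 24, 36 and 48 (Protocol 9.1.3), then every 12 weeks to Week 96 (SAP 1.2). Days to a visit at week w are 7w + 1, which matches the target days in SAP 2.5.2 (169, 337 and 589 for Weeks 24, 48 and 84).

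**Assumptions.** Bottles hold 30 tablets, and supply is rounded up to whole bottles: 30 tablets for a 4-week interval, 90 for a 12-week one. Last intake is missing. Leftovers are returned except where stated.

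**Reading A: drug dispensed at the last attended visit counts and is not returned.** With true adherence a and unreturned supply S:

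score = 100 × (a × 7w + S) / (7w + 1)

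Lowest a scoring 95% = (0.95 × (7w + 1) − S) / 7w

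At a = 80% and Week 48: (0.80 × 336 + 90)/337 = 358.8/337 = 106.5%.

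**Reading B: last-visit dispensing is not counted, and only the previous interval's bottles are unreturned.** With p the week of the previous dispensing visit:

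score = 100 × (a × 7p + S) / (7w + 1)

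At a = 80% and Week 48: (0.80 × 252 + 90)/337 = 291.6/337 = 86.5%.

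| Lost after | Days | A: score at 80% | A: lowest true adherence reaching 95% | B: score at 80% |
|---|---|---|---|---|
| Week 4 | 29 | 180.7% | any | 103.4% |
| Week 12 | 85 | 184.9% | any | 88.0% |
| Week 24 | 169 | 132.8% | 42.0% | 93.0% |
| Week 48 | 337 | 106.5% | 68.5% | 86.5% |
| Week 84 | 589 | 95.1% | 79.9% | 83.7% |

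Under B the 95% line is reached from a true adherence of (160.55 − 90)/84 = 84.0% at Week 24, (320.15 − 90)/252 = 91.3% at Week 48 and (559.55 − 90)/504 = 93.2% at Week 84.

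**Poor adherence under A.** At 50% the score is 103.0% at Week 24, but 85.4% at Week 36, 76.6% at Week 48 and 65.2% at Week 84. The last three are non-adherent.

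**Bottle size under A.** With 28-tablet bottles, 80% scores 177.9%, 104.7% and 94.1% at Weeks 12, 48 and 84, so the Week 84 case falls below the cut. With 90-tablet bottles the scores equal those for 30.

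**Late switchers under A.** Their count restarts at the Week 52 switch, so days at Weeks 60, 72 and 84 are 57, 141 and 225. Ninety unreturned tablets add 90/57 = 158, 90/141 = 64 and 90/225 = 40 points.

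**Derivation (ii).** If it is cut at the last visit before the missing bottles, 80% scores 67.2/85 = 79.1% (Week 12), 268.8/337 = 79.8% (Week 48) and 470.4/589 = 79.9% (Week 84). If the one tolerated 30-tablet bottle counts as taken, it can still add 30/29 = 103 points at Week 4, 30/85 = 35 at Week 12, 30/337 = 8.9 at Week 48 and 30/673 = 4.5 at Week 96.

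**The case against.** The large figures need reading A. Drug is also dispensed at Week 96, and visits are then six months apart. If end-visit dispensing counted there, a completer who continues would gain about 180/673 = 27 points, which cannot be intended. So the sum plausibly leaves out dispensing at the visit that closes the denominator. This is a fair argument, and for that reason reading A is only an assumption here. It does not settle the wording, because for a withdrawn subject the time point of interest may still be Week 96, and an earlier dispensing falls before it.

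The affected group is also limited. The last-visit fallback applies only when the subject discontinued and last intake is missing. Those who stop before Week 96 are to attend an early discontinuation visit within 72 hours, with drug accountability (Protocol 9.1.5.1, 10.2), and those who return their drug there are unaffected.

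The uses are modest. SAP 1.3 and 4.4.1 make the Week 96 analysis descriptive, and SAP 4.5.1 leaves the Week 48 primary endpoint analysis out of this SAP. The only adherence rule that changes an analysis set already uses derivation (ii). All of this stands and limits the weight of the point. It does not remove it: as written, derivation (i) can give a wrong value, and nothing keeps that value out of the >95% class in SAP 2.7.1 and 4.6.2.

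**Conclusion.** The point holds in a limited form. Under derivation (i), a subject who stops without returning drug can be classed above 95% adherent despite lower true adherence. The size depends on timing and on whether last-visit dispensing counts. If it does, 80% true adherence scores about 133%, 107% and 95% after loss at Weeks 24, 48 and 84. If it does not, inflation is far smaller, and the >95% class is reached mainly after very early loss or when true adherence is already near the cut. All figures rest on an assumed bottle size.

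A reader might infer that every subject lost to follow-up scores near or above 100%, or that the reported adherence and its link to rebound are distorted by a known amount. The documents support neither. Late losses with poor adherence stay at or below 95%, and neither the bottle size nor the number lost without a last-intake date is given. A reader might also infer that derivation (i) definitely feeds the subgroup; the SAP leaves that open.

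**What to change.** For the adherence subgroup in SAP 2.7.1 and the blip/rebound comparison in SAP 4.6.2, compute adherence only over dispensing intervals closed by a return count. Numerator and denominator should end at the same accountability visit, and drug dispensed at or after that visit should be left out. At minimum, name derivation (ii) for both analyses and state whether its tolerated missing bottle counts as taken, since that matters for early losses. Subjects with no closed interval go to the existing missing/unknown class. Keep derivation (i) as a sensitivity summary.

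The cost is SAP wording and the reprogramming of one derived variable; no new data are needed. The drawback is that some subjects move to unknown, and that may itself be informative. Report their number and virologic outcome alongside the two adherence classes.
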